15.3. EXPLORATORY EFFICACY

15.3.1. EXPLORATORY EFFICACY VARIABLES & DERIVATIONS

15.3.1.1. AUC_{0-24h} FEV₁ on Day 3

 $AUC_{0.24h}$ FEV₁ after evening dose on Day 3 is defined and derived similarly to secondary endpoint in section 15.2.1.3. Parameters will be calculated over 24 hours (on Day 4 of each treatment period). If patient misses hours 12 and 24 then the $AUC_{0.24h}$ is set to missing.

Document: Z:\RPL554\UYA25849\Biostatistics\Documentation\SAP\Verona RPL554-CO-204 SAP v1.0

Author: [name] Version Number: 1.0

Version Date: [18OCT2018]

Template No.: CS_TP_BS016 Revision 5 Reference: CS_WI_BS005

Effective Date: 01Apr2018

Page 34 of 50

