Whole body plethysmography	X							X						X		X					
Pharmacokinetic samples	X		X		X	X	X		X	X	X		X		X ^c						
Hematology and biochemistry																					X
Dyspnea scale	X		X	X	X																X
Adverse events										T	hrougho	out									

Abbreviations: ECG=electrocardiogram; h=hour; m=minutes

- [a] Procedures performed prior to discharge from the study center on the morning of Day 4, 12 hours after final RPL554 dosing on Day 3
- [b] Can be performed any time prior to discharge
- [c] Perform pharmacokinetic sample prior to dosing

Verona Pharma plc CONFIDENTIAL Page 34 of 66

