6.3.3.3 Post-Dose Assessments

- 12-lead ECGs at 2 and 24 hours (±10 minutes)
- Vital signs at 30 minutes and 1, 2, 4, 6, 8 and 24 hours (± 10 minutes)
- Spirometry at 5 (\pm 1), 15 (\pm 5) and 30 minutes and 1, 1.5, 2, 4, 6, 8, 12, 13, 14, 16, 23 and 24 hours after the morning dose (the latter assessments all \pm 10 minutes)
- Whole body plethysmography at 1.25, 8.25 and 12.25 hours (± 10 minutes)
- Dyspnea scale at 5 (\pm 1), 15 (\pm 5), and 30 (\pm 10) minutes and 24 hours (\pm 10 minutes)
- Questioning for adverse events
- Blood samples for pharmacokinetics at 5 (\pm 1), 30 and 45 minutes and 1, 1.5, 2, 4, 8 and 12 hours (the latter assessments all \pm 10 minutes)
- Blood sample for laboratory safety tests (hematology and biochemistry) at 24 hours (±10 minutes)
- Brief physical examination prior to discharge (Day 4)

The 24-hour assessments will be performed in the morning on Day 4 prior to discharge from the study center.

Patients will be instructed to return in 7 to 14 days (taken from last dose of study medication on Day 3) for the next visit, or if Treatment Period 3, to return in 4 to 10 days (from Day 4) for the end of study visit. Early terminated patients should have an End of Study Visit.

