7.2 Efficacy/Pharmacodynamic Assessments

7.2.1 Pulmonary Function Tests

Spirometry (FEV₁ and FVC) will be performed at Screening, the end of study visit and the following time points in each treatment period:

- Day 1: 1 hour and immediately pre-dose; 5, 15 and 30 minutes and 1, 1.5, 2, 4, 6, 8 and 12 hours post-dose
- Day 2: pre-dose; 15 and 30 minutes and 1, 2, 3 4 hours and 12 hours post-dose
- Day 3: pre-dose; 5, 15 and 30 minutes and 1, 1.5, 2, 4, 6, 8, 12, 13, 14, 16, 23 and 24 hours post-dose.

Post-dose measurements will be taken in relation to the morning dose of tiotropium/olodaterol and RPL554 or placebo. The 12-hour measurement will therefore be taken pre-dose before the evening dose of RPL554 or placebo. The 24-hour measurement on Day 3 will be taken in the morning on Day 4 prior to discharge from the study center.

Spirometry assessments will be made in accordance with ATS/ERS guidelines (Miller et al, 2005). At all timepoints, three technically acceptable measurements should be made and recorded. Spirometry assessments may be performed up to eight times to obtain three acceptable readings. The highest FEV_1 and FVC readings from each assessment will be used for analysis even if the FEV_1 and FVC values come from two different forced exhalations.

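### The SAP starts the exploratory 24-hour FEV1 AUC at the Day 3 evening dose, but scheduled spirometry ends 12 hours after that dose

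*SAP*

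**What the plan says.** SAP 15.3.1.1 describes the 24-hour AUC of FEV1 as "after evening dose on Day 3 is defined and derived similarly" to the endpoint in SAP 15.2.1.3, which concerns Day 1. On the interval it says "Parameters will be calculated over 24 hours (on Day 4 of each treatment period". Its missing-data rule begins "If patient misses hours 12 and 24 then the", and the AUC is then set to missing.

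The protocol times Day 3 spirometry from the morning dose:

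- Protocol 7.2.1 lists readings up to "1.5, 2, 4, 6, 8, 12, 13, 14, 16, 23 and 24 hours post-dose" and states the clock: "Post-dose measurements will be taken in relation to the morning dose of tiotropium/olodaterol" and the nebulized study medication.
- Protocol 6.3.3.3 gives the last readings as "13, 14, 16, 23 and 24 hours after the morning dose".
- Protocol Table 4, footnote [a], places the Day 4 procedures "12 hours after final RPL554 dosing on Day 3".

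Protocol 9.3.3 lists the endpoint as belonging to Day 3 and mentions no evening dose. SAP 3.3 records no change from the protocol's analysis.

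**The concern.** An AUC over 24 hours needs readings that span 24 hours from its time 0. If time 0 is the evening dose, the scheduled readings stop halfway. The part left out is the morning profile, which holds the response to tiotropium/olodaterol and to the morning dose of RPL554. A 12-hour evening average reported as a 24-hour one would answer a different question, and its treatment ratio could differ from the intended one.

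The phrase is easy to take at face value, because the SAP separates the two doses elsewhere. SAP 15.2.1.2 ties the 4-hour AUC to the morning dose, and SAP 15.2.1.5 builds the evening peak from the 13, 14 and 16-hour readings. The exploratory objective speaks of 24 hours after three days of dosing and names no starting dose, so it does not settle the matter.

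**Working it through.** No power or error-rate formula applies. The check is timeline arithmetic.

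**Inputs**

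- Evening dose: 12 h (±30 min) after the morning dose (Protocol 5.4.2).
- First dose of the day: between 07:00 and 11:00 (Protocol 5.4.2).
- Day 3 spirometry on the morning clock: pre-dose; 5, 15 and 30 min; 1, 1.5, 2, 4, 6, 8, 12, 13, 14, 16, 23 and 24 h (Protocol 6.3.3.3 and 7.2.1). The later readings have a ±10 min window.
- The 12 h reading is taken just before the evening dose (Protocol 7.2.1).

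**Reproducing the plan's own figure**

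Last reading minus evening dose: 24 − 12 = 12 h. This agrees with Table 4, footnote [a]. It also agrees with the SAP's trough definition (15.2.1.1), which uses 11 and 12 h after the evening dose: 11 + 12 = 23 and 12 + 12 = 24 on the morning clock.

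With the permitted windows:

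- shortest: 24 h − 10 min − 12.5 h ≈ 11.3 h
- longest: 24 h + 10 min − 11.5 h ≈ 12.7 h

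**Converting the readings to an evening clock (morning hour − 12)**

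| Morning clock (h) | 12 | 13 | 14 | 16 | 23 | 24 |
|---|---|---|---|---|---|---|
| Evening clock (h) | 0 | 1 | 2 | 4 | 11 | 12 |

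**Comparing the two anchors**

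| Time 0 | Nominal points | Hours covered | Share of 24 h |
|---|---|---|---|
| Day 3 morning dose | 16 | 24 | 24/24 = 100% |
| Day 3 evening dose | 6 | 12 | 12/24 = 50% |

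The evening anchor drops 16 − 6 = 10 points: the morning pre-dose reading and everything from 5 min to 8 h.

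**Where a 24-hour evening interval would end**

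A first dose at 07:00 to 11:00 puts the evening dose at 19:00 to 23:00. Adding 24 h gives 19:00 to 23:00 on Day 4. The last spirometry is on the morning of Day 4, nominally 07:00 to 11:00, before discharge. No spirometry is scheduled between 12 and 24 h after the evening dose.

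**The missing-data rule**

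On the morning clock, hours 12 and 24 are both scheduled readings. On the evening clock, hour 12 is the final reading and hour 24 is missing for every patient, so the rule cannot work as a check on the end of the interval.

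**The case against.** The strongest reply is that one phrase is wrong and everything around it shows what was meant:

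- The SAP heading and the protocol endpoint both place the AUC on Day 3.
- The SAP paragraph ends the interval on Day 4, and its rule names hours that fit the morning schedule.
- SAP 15.3.3 again speaks of average FEV1 on Day 3 over 24 hours.
- The cross-reference to 15.2.1.3 leads on to 15.2.1.2, whose formula counts time from the Day 3 morning dose. The link is imperfect, because 15.2.1.3 adapts the method to Day 1.
- With no declared change from the protocol, a deliberate move to the evening dose is implausible.

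This stands. A careful statistician would probably recover the morning anchor, and all the data for it are collected. A reader might infer that the endpoint cannot be computed at all, or that the program will integrate only 12 hours. The documents establish neither. They show a definition that contradicts the schedule, not how it would be programmed.

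A reader might also infer that the reported average would be halved, as a 12-hour area divided by 24 hours. The SAP has no such rule. Section 15.2.1.2 divides by the actual elapsed time to the closing reading, so a consistent evening clock divides about 12 hours of area by about 12 hours. Halving would need an area counted from the evening dose over a time counted from the morning dose, and the SAP does not prescribe that mixture.

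**Conclusion.** The evening-dose anchor in SAP 15.3.1.1 is wrong against the protocol schedule. Taken literally, it covers 12 of 24 hours with six of the 16 nominal points, omits the morning-dose response, and makes the missing-data rule unworkable. The surrounding text indicates that the morning dose was intended, so this is a drafting error to correct and not a gap in data collection.

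The effect is limited. The endpoint is exploratory and lies outside the primary and secondary testing in SAP 7.4. The primary result, the error rate and the sample size do not depend on it.

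Two assumptions apply. First, only scheduled readings are counted; SAP 6.3 allows unscheduled ones to contribute, but none is planned after the evening dose to fill the gap. Second, the SAP cites protocol version 2.0, while the protocol reviewed describes itself as the first version. The schedule is taken to be the same in both. The SAP's own trough and evening-peak definitions support this, since they use the same clock.

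**What to change.** In SAP 15.3.1.1:

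1. Define the endpoint as the AUC of FEV1 from 0 to 24 h after the morning dose on Day 3.
2. State that the Day 3 morning pre-dose value sits at time 0, that all readings through 24 h (Day 4) are used, and that the area is divided by the actual time of the 24 h reading since the morning dose. The Day 1 pre-dose value remains the baseline in the model.
3. Point the cross-reference to SAP 15.2.1.2 instead of the Day 1 section 15.2.1.3.

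In SAP section 12 (time to first rescue medication), the last spirometry of the period is placed 24 h after the third evening dose. Change this to 24 h after the Day 3 morning dose.

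The cost is a few phrases in the SAP. No new data, visits or analyses are needed. Making the change before unblinding avoids having to reinterpret the definition afterwards.

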15.3.1.2. Change from baseline in dyspnea scale

An 11-point Likert scale will be utilized, with patients being asked the following question by a blinded member of staff: "On a scale of zero to ten, please rate your current shortness of breath, with zero indicating no shortness of breath and ten indicating the worst shortness of breath that you can imagine". This scale will be an instantaneous measurement of their dyspnea at that moment, and not reflective. It will be administered on Day 1 pre-dose and 5, 15, and 30 minutes post-dose; and on Day 3 pre-dose and 5, 15, 30 minutes and 24 hours post-dose. Baseline will be considered the pre-dose assessment on Day 1 of each treatment period and change from baseline will be assessed at 30 min post-dose on Day 1 and Day 3 and 24hours post-dose on Day 3.

15.3.2. MISSING DATA METHODS FOR EXPLORATORY EFFICACY VARIABLE(S)

Missing data will not be imputed similarly to primary endpoint, where applicable (see section 15.1.2).

15.3.3. ANALYSIS OF EXPLORATORY EFFICACY VARIABLES

The analysis relating the to the average FEV_1 on Day 3 over 24 hours will be analyzed in the same way as the primary endpoint.

Dyspnea score and the change in dyspnea score will be summarized at each timepoint of interest (30 min post-dose on Day 1 and Day 3 and 24hours post-dose on Day 3).

In addition, Wilcoxon signed rank test for pair-wise comparisons between baseline and the relevant post-baseline assessment, will be applied to identify differences.

The SAS® procedure NPAR1WAY will be used as follows, to conduct the Wilcoxon rank sum test:

Document: Z:\RPL554\UYA25849\Biostatistics\Documentation\SAP\Verona RPL554-CO-204 SAP v1.0

Author: [name] Version Number: 1.0

Version Date: [18OCT2018]

Template No.: CS_TP_BS016 Revision 5 Reference: CS_WI_BS005

Effective Date: 01Apr2018

Page 35 of 50

PROC NPAR1WAY DATA=... WILCOXON; CLASS TREATMENT; VAR DIFF; EXACT WILCOXON; RUN;

where

DIFF = difference in dyspnea score between baseline and each post-baseline assessment TREATMENT = treatment group

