2.3 Exploratory Objectives

- To assess the dose response of RPL554 on peak and average (measured as AUC over 12 hours) after morning dose on Day 3, and morning trough FEV₁ (mean of values at 11 and 12 hours after last dose of RPL554) on Day 4, when dosed in addition to tiotropium/olodaterol
- To examine the effect of RPL554 on top of tiotropium/olodaterol on average (measured as AUC) FEV₁ over 24 hours after 3 days of dosing
- To examine the effect of RPL554 on top of tiotropium/olodaterol on a Likert dyspnea scale

[figure not shown]
Verona Pharma plc CONFIDENTIAL Page 17 of 66

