3 INVESTIGATIONAL PLAN

3.1 Overall Study Design and Plan Description

This is a Phase II, randomized, double blind, placebo controlled, complete block three-way crossover study to investigate treatment with nebulized RPL554 and tiotropium/olodaterol Respimat[®] in patients with moderate to severe COPD. It is planned to randomize approximately 70 patients at up to four study centers. The study comprises the following, as shown in Figure 1: Screening, three treatment periods each lasting 3 days and an end of study visit. The procedures performed at each visit are summarized in Section 6 and the study assessments are described in Section 7.

Figure 1 Study Flow Chart

Patients will be screened for eligibility, including a reversibility test with salbutamol (in UK) /albuterol (in US) and ipratropium between 7 and 14 days before the first dose of study treatment.

Eligible patients will then attend the clinic for three separate treatment periods (Treatment Periods 1 to 3), with each lasting 3 days and separated by a 7 to 14-day washout period (taken from last dose of study medication). Patients will be randomized pre-dose on Day 1 of Treatment Period 1. During each treatment period, patients will be present at the study center from the morning of Day 1 until the morning of Day 4.

In each treatment period, patients will receive an open label dose of tiotropium/olodaterol from a Respimat® device followed immediately (starting within 2 minutes) by a double-blind dose of either RPL554 or placebo (depending on treatment sequence) from a nebulizer in the morning on Day 1, Day 2 and Day 3. The dose of RPL554 or placebo will be repeated in the evening on Day 1, Day 2 and Day 3.

The assessments performed in each treatment period will be the same. Lung function (FEV₁ and forced vital capacity [FVC]) will be measured by spirometry pre-dose and up to 12 hours post-dose on Days 1 and 2 and up to 24 hours post-morning dose on Day 3 (i.e. Day 4). Whole body plethysmography will be performed pre-dose and 1.25 hours post-dose on Day 1, and pre-dose and 1.25, 8.25 and 12.25 hours post-dose on Day 3. Vital signs will be measured pre-dose and up to 12 hours post-dose on Day 1, up to 12 hours post-dose on Day 2 and up to 24 hours post-dose on Day 3 (i.e. Day 4). Electrocardiograms (ECG) assessments will be performed pre-dose and up to 4 hours post-dose on Day 1, at 2 hours post-dose on Day 2 and

Verona Pharma plc CONFIDENTIAL Page 18 of 66

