9.3.3 Exploratory Endpoints

- AUC_{0-24h} FEV₁ on Day 3
- Change from baseline in Likert dyspnea scale

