15.1.3. PRIMARY ANALYSIS OF PRIMARY EFFICACY VARIABLE(S)

The primary efficacy objective of the study is to show that at least 1 RPL554 + tiotropium/olodaterol treatment group (RPL554 6mg + tiotropium/olodaterol and/or RPL554 1.5 mg + tiotropium/olodaterol) will increase peak FEV₁ (change from Baseline) compared to RPL554 placebo + tiotropium/olodaterol at Day 3 (measured in first 4 hours after morning dosing) by rejecting the null hypothesis described below at significance level α =0.05 level (2-sided):

$$H_0$$
: $\mu_i = \mu_0$ versus H_1 : $\mu_i \neq \mu_0$

where μ_j and μ_0 are the mean change from Baseline in peak FEV₁ at Day 3 (measured in first 4 hours after morning dosing) for 1 RPL554 + tiotropium/olodaterol treatment group (RPL554 6mg + tiotropium/olodaterol and/or RPL554 1.5 mg + tiotropium/olodaterol) and RPL554 placebo + tiotropium/olodaterol respectively.

Document: Z:\RPL554\UYA25849\Biostatistics\Documentation\SAP\Verona RPL554-CO-204 SAP v1.0

Author: [name] Version Number: 1.0

Version Date: [18OCT2018]

Template No.: CS_TP_BS016 Revision 5 Reference: CS_WI_BS005

Effective Date: 01Apr2018

Page 28 of 50

An ANCOVA will be used to test the hypothesis with change from baseline FEV₁ to peak FEV₁ (measured in first 4 hours after morning dosing) on Day 3 as response variable, and treatment, treatment period and baseline FEV₁ as covariates. Analyses will be implemented using the SAS® procedure MIXED as follows:

```
PROC MIXED DATA = ...;

CLASS SUBJECT PERIOD TREATMENT;

MODEL CHG = TREATMENT PERIOD BASELINE;

RANDOM USUBJID;

LSMEANS TREATMENT / CL DIFF;

RUN;

where CHG = difference in log (peak FEV1) - log (baseline FEV1) i.e. log (peak FEV1 / baseline FEV1)

TREATMENT = treatment group (1.5 mg RPL554, 6 mg RPL554 and placebo)

PERIOD = treatment period (treatment period 1, 2 and 3)

BASELINE = log (baseline FEV1)

USUBJID = subject ID
```

The primary comparison will be the contrast (difference in least squares mean [LSMEAN]) between 6 mg RPL554 and placebo on Day 3 (in first 4 hours after morning dosing).

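### The dyspnea analysis names a signed-rank test against baseline but codes an unpaired test across treatments; neither compares RPL554 with placebo within patient

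*SAP*

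**What the plan says.** The protocol's exploratory objective (Section 2.3) is: "To examine the effect of RPL554 on top of tiotropium/olodaterol on a Likert dyspnea scale". The endpoint in Section 9.3.3 is "Change from baseline in Likert dyspnea scale". Protocol Section 9.4.5 prescribes no test for it.

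SAP Section 15.3.1.2 fixes the reference value: "Baseline will be considered the pre-dose assessment on Day 1 of each treatment period". Change is assessed at 30 minutes on Days 1 and 3, and at 24 hours after the Day 3 morning dose.

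SAP Section 15.3.3 plans summaries at these timepoints and, in addition, a "Wilcoxon signed rank test for pair-wise comparisons between baseline and the relevant post-baseline assessment". The next sentence says the SAS "procedure NPAR1WAY will be used as follows, to conduct the Wilcoxon rank sum test". The code is "CLASS TREATMENT; VAR DIFF; EXACT WILCOXON; RUN", where DIFF is the change in dyspnea score from baseline.

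**The concern.** The two sentences describe different tests with different null hypotheses. A signed-rank test of post-dose against baseline asks whether scores moved during a treatment period. A rank-sum test of change by treatment asks whether the treatments differ, and assumes that the groups contain different people. The code given cannot perform the test named in the text, so two programmers could report different p-values from the same plan.

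Neither test fits the question. We read an effect of RPL554 on top of tiotropium/olodaterol as a contrast with placebo on the same background. In a crossover that contrast should be made within patient, which is also how Protocol Section 3.2 justifies the design. The more serious practical risk lies in the text version: a significant fall in dyspnea during RPL554 periods could be reported as a symptom benefit when placebo periods show the same fall.

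**Working it through.** **What each test compares.**

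1. *Test in the text.* Baseline is specific to the period, so the comparison is of one treatment with its own pre-dose value. Protocol Section 3.1 states: "In each treatment period, patients will receive an open label dose of tiotropium/olodaterol". A change from baseline therefore mixes the effect of that background treatment with any effect of RPL554.
2. *Test in the code.* SAP Section 15.1.3 defines "TREATMENT = treatment group (1.5 mg RPL554, 6 mg RPL554 and placebo"; SAP Section 7.1 and Appendix 1 list the same three groups. With three classes and no subsetting, NPAR1WAY gives one overall Kruskal-Wallis test, with no contrast of a dose with placebo. It has no patient or period term.
3. *Other sources.* The sentence in SAP 15.3.3 that refers back to the primary analysis covers only 24-hour average FEV₁. SAP Section 7.4 covers primary and secondary endpoints only. No other dyspnea test is given.

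**Illustration.** The documents state no dyspnea SD, correlation or effect size, so there is no plan figure to reproduce. From the documents: about 70 patients, three periods, two-sided 5% level. Assumed: change scores rounded to integers, SD 1.2 points, within-patient correlation of changes ρ from 0 to 0.7, and an effect of 0 or 0.5 points.

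*Signed-rank against baseline in an RPL554 period, when RPL554 adds nothing* (4,000 simulated trials):

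| Background change (points) | 0 | 0.25 | 0.5 | 1.0 |
|---|---|---|---|---|
| Trials with p<0.05 | 4% | 37% | 91% | 100% |

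Hand check at 0.5 points: 0.5 × √70 / 1.2 = 3.49, and Φ(3.49 − 1.96) = 94%. Rounding and the use of ranks account for the small shortfall in the simulation.

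*Comparison of 6 mg with placebo* (5,000 trials for size; 3,000 for power, with only 6 mg shifted by 0.5 points):

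| ρ | 0 | 0.1 | 0.3 | 0.5 | 0.7 |
|---|---|---|---|---|---|
| Size, unpaired rank-sum | 4.9% | 4.2% | 2.0% | 0.9% | 0.2% |
| Power, unpaired rank-sum | 64% | 65% | 67% | 68% | 72% |
| Power, signed-rank on RPL554-minus-placebo change | 64% | 68% | 79% | 90% | 98% |
| Power, crossover model | 66% | 70% | 81% | 90% | 98% |

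The paired methods kept a size of 4.5% to 5.6% throughout. The simulated crossover model had fixed patient, treatment and period, but no baseline term.

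The fall in size has a simple cause. The true variance of the treatment difference is (1 − ρ) times the variance that the unpaired test assumes, so its size is about 2[1 − Φ(1.96/√(1 − ρ))]. At ρ = 0.3 this is 2[1 − Φ(2.34)] = 1.9%, and at ρ = 0.5 it is 2[1 − Φ(2.77)] = 0.6%, close to the simulated values.

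*Three-group test as coded*, in a separate run of 4,000 trials with SD 1.5 and both doses shifted by 0.5 points:

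| ρ | 0 | 0.3 | 0.5 | 0.7 |
|---|---|---|---|---|
| Size, three-group test | 5.2% | 1.5% | 0.4% | <0.1% |
| Power, three-group test | 47% | 43% | 42% | 38% |
| Power, paired signed-rank | 46% | 61% | 74% | 92% |

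**Which ρ is plausible?** A stable patient level alone gives a correlation of changes near 0, because subtracting the period's own baseline removes it. A positive ρ needs something more, such as a shared patient response to tiotropium/olodaterol.

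**The case against.** *The SAP may intend two analyses, one within and one between treatments.* This is possible. On that reading the first has no code and the second no stated rationale, and there is still no within-patient contrast with placebo.

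*The three-group reading is an inference.* The input dataset is left open, and a rank-sum test is normally a two-sample test, so the program might be run on pairs of treatments. That would supply a contrast of dose with placebo, but still an unpaired one.

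*The percentages depend on an assumed SD.* They do. A 0.5-point background change is significant in 91% of trials at SD 1.2, but in 75% at SD 1.5, about 54% at 2.0 and about 35% at 2.5. Rank-sum power for 0.5 points at SD 2.0 is about 30%, falling to 18% as ρ rises. The levels move; the pattern does not.

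*The harm may be nil.* At ρ = 0 the unpaired test has nominal size and loses almost no power, and at positive ρ it errs on the conservative side. This stands for the coded test. It does not help the test against baseline, whose problem is the missing control.

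*The objective does not mention placebo, unlike the primary objective, and the endpoint is exploratory.* Both are true. The placebo contrast is our reading, and the point bears only on the dyspnea result.

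**Conclusion.** The concern holds. As written, SAP Section 15.3.3 offers two different tests, and neither estimates the effect of an RPL554 dose against placebo within patient. This follows from the text and code alone.

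The test against baseline can be significant in most trials through the background treatment alone. The unpaired test loses anything from almost no power to a large amount, depending on a correlation that the documents do not give. Those sizes rest on the assumed SD, correlation and effect. The section should be corrected, but no primary or secondary conclusion depends on it.

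**What to change.** Delete the NPAR1WAY code and state one comparison in both text and code: each RPL554 dose against placebo, within patient, at 30 minutes on Days 1 and 3 and at 24 hours.

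- **Main analysis:** a crossover model for change in dyspnea score with treatment, period, patient and period baseline, on the additive scale. Scores can be 0, so the log-scale FEV₁ model cannot simply be copied. The SAP should also say whether patient is fixed (as in Protocol 9.4.5) or random (as in SAP 15.1.3).
- **Nonparametric check:** a signed-rank test on each patient's RPL554-minus-placebo change, noting that it does not adjust for period.
- **Change from baseline within a treatment:** keep it as descriptive only.

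The cost is SAP wording and one program. No new data are needed. The change should be made before unblinding, so that the choice of test cannot depend on the results.
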